01.12.2024

Comparative Evaluation of the Possible Effects of Platelet Rich Plasma (Prp) and Low Level Laser (Biolase) on Postoperative Complications and Wound Healing After Extraction of Impacted Wisdom Teeth

Study Protocol

The study was conducted on a total of 30 patients aged between 18 and 40 years who applied to the XXX Oral and Maxillofacial Surgery Department Clinic for bilateral, similar position, half mucosa and bone retention lower impacted wisdom teeth extraction. First, clinical and radiological evaluations were performed on the patients. In the clinical evaluation, systemic status, tooth deficiency, occlusion and the status of the impacted tooth were evaluated. Panoramic film was taken for radiographic evaluation.

Inclusion criteria;

- Individuals aged 18 years and over,
- Patients with partially impacted wisdom teeth,
- Individuals with systemic status according to ASA classification as ASA0 and ASA1,
- Individuals who have not used any medication in the last two weeks,
- Individuals who do not have a missing lower second molar.

Exclusion criteria for the study;

- Individuals with mouth opening less than 25 mm for various reasons,
- Pregnant and breastfeeding individuals,
- Individuals who do not come to postoperative check-ups,
- Individuals using different medications other than the recommended medication.

Individuals who were allergic to the study drugs and the materials to be used were excluded from the study. All patients were included in the study after detailed information about the study was provided and a consent form was signed by the patient. The study was initiated after permission was obtained from the XXX University Ethics Committee. (Decision No:) All operations were performed by the same physician in the operating room of the XXX University Faculty of Dentistry, Department of Oral and Maxillofacial Surgery, adhering to surgical principles and sterilization rules, under equal operating conditions.

Study groups; Randomized, prospective, split mouth and single core, 30 patients in total were divided into two groups.

Study groups were determined as follows:

- A. Platelet-rich plasma (PRP) applied group.
- B. Low-level laser therapy (LLLT) applied group.

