First group (one side of the same patients): Platelet-rich plasma (PRP, initially 1200 revolutions per minute (rpm), 10 minutes later 2000 rpm for 10 minutes); second group (other side of the same patient): low-level laser treatment, diode laser (Ezlase 940; Biolase Technology, Inc., Irvine, CA) 100 mW (0.1 W) was applied for a total of 120 seconds. After the surgery, these two groups (methods) were applied to the extraction socket at different times (with a 2-week interval between each surgery). Both surgical sites were sutured with 3/0 silk suture (18 mm, 3\8 sharp, 75 cm black, Dağsan Silk Suture). It was randomly determined which material would be used first on which side. The other side was operated on after 2 weeks. Using an automatic centrifuge machine, PRP was initially prepared at 1200 rpm for 10 minutes and then 3 layers were created. 1) An upper straw-colored PPP (platelet-poor plasma). 2) A middle cloudy layer rich in platelets. 3) A lower layer rich in red blood cells. The straw-colored upper layer was collected together with the cloudy layer and centrifuged again at 2000 rpm for 10 minutes. Leukocyte-rich PRP was formed at the bottom of the test tube; the upper PPP was discarded using a pipette. 1 ml (10%) calcium chloride was added to the Platelet Rich Plasma for activation. (50 microliters of 10% calcium chloride is added for 1.0 mL of PRP). Gel was formed after 10 minutes. This layer consisting of approximately 2 ml of PRP was then placed in the extraction socket within 2 minutes after surgical removal of the mandibular third molar. The second group received a single session of intraoral 940 nm diode laser (BIOLASE) for 120 seconds immediately after suturing.

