All statistical analyses were performed in a statistical software program (SPSS version 26.0, IBM Corp.). Mean, standard deviation, median, minimum and maximum values were calculated for descriptive statistics. Categorical data were shown with frequency and percentage. The conformity of the data to normal distribution was evaluated by examining the Shapiro-Wilk test and histograms. Comparisons between the two treatment groups were made with the Student-T test for data suitable for normal distribution, while the Mann-Whitney U test was used for data not suitable for normal distribution. In order to find statistical differences in the time-dependent changes in the measured data in both treatment groups, repeated measures ANOVA test was used for normally distributed data and Bonferroni test was used for post-hoc comparisons. Friedman test was applied to non-normally distributed data and Dunn-Bonferroni test was used for post-hoc comparisons. Chi-square test was applied for comparison of categorical data. Significance level was determined as $p<0.05$.

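### The plan compares PRP with laser using independent-samples tests, although every patient receives both treatments and the data are paired.

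*Combined protocol and SAP*

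**What the plan says.** The Study Protocol describes the design as "Randomized, prospective, split mouth" and enrols 30 patients with bilateral impacted lower third molars in similar positions. The treatment description puts both treatments in each patient: "First group (one side of the same patients): Platelet-rich plasma" and "second group (other side of the same patient): low-level laser treatment". The two operations are 2 weeks apart, and order and side were randomised: "It was randomly determined which material would be used first on which side".

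For PRP versus laser, the Statistical Analysis Plan gives two branches:

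- Normal data: "Comparisons between the two treatment groups were made with the Student-T test for data suitable for normal distribution". It does not say whether the paired or the independent form is meant.
- Other data: "Mann-Whitney U test was used for data not suitable for normal distribution".

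Repeated measures ANOVA and the Friedman test are assigned to change over time in the treatment groups. For categorical data: "Chi-square test was applied for comparison of categorical data". No paired t-test, Wilcoxon signed-rank test, McNemar test or mixed model with a patient effect appears anywhere.

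**The concern.** Each outcome yields 30 matched pairs, not two independent samples of 30. A test for independent samples computes the standard error as if a patient's two sides were unrelated. If they are positively correlated, that standard error is too large, the confidence interval too wide and the p-value too high. Positive correlation is plausible here, because the same person scores pain on the same scale and mouth opening is measured in the same jaw.

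The study question is the contrast between two active treatments, so what is at stake is a real difference being missed. With 30 patients and no sample-size justification in the documents, the pairing is the main source of precision, and the stated tests discard it. The issue touches the PRP-laser comparisons of pain, edema and mouth opening. The within-treatment tests over time are not affected by it.

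**Working it through.** **Inputs from the documents.** 30 patients, both sides treated in each (Study Protocol); significance level 0.05 (Statistical Analysis Plan).

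**Assumptions, because the documents are silent.** Two-sided testing, 30 complete pairs, equal SDs on the two sides, bivariate normal data, a true difference d = 0.5 SD, and a within-patient correlation ρ between -0.2 and 0.7. The plan states no power, SD or effect, so there is no figure of its own to reproduce.

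**Step 1: the standard error.** With SD σ and n pairs, the variance of the mean difference is 2σ²(1-ρ)/n. The unpaired test uses 2σ²/n. Apart from a small difference in the t quantile, its confidence interval is therefore too wide by 1/√(1-ρ): 1.20 times at ρ = 0.3, 1.41 at 0.5 and 1.83 at 0.7.

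**Step 2: actual type I error of the unpaired test.** In large samples this is 2[1 - Φ(1.96/√(1-ρ))]. At ρ = 0.5, 1.96/√0.5 = 2.77, which gives 0.0056. At ρ = 0.3 the formula gives 0.0191. Simulation with n = 30 gives 0.007 and 0.020.

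**Step 3: power of the paired t-test.** The noncentrality is d√n/√(2(1-ρ)) on 29 degrees of freedom. At ρ = 0.5 it is 0.5 × √30/√1 = 2.74, giving power 0.754. The same formula gives 0.401, 0.465, 0.609 and 0.927 at ρ = -0.2, 0, 0.3 and 0.7.

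**Step 4: simulation of both forms** (200,000 trials per cell for t-tests, 40,000 for rank tests):

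| ρ | Type I error, unpaired t | Power, unpaired t v paired t | Type I error, Mann-Whitney | Power, Mann-Whitney v signed-rank |
|---|---|---|---|---|
| -0.2 | 0.073 | 0.48 v 0.40 | 0.074 | 0.46 v 0.39 |
| 0 | 0.050 | 0.48 v 0.47 | 0.048 | 0.46 v 0.46 |
| 0.3 | 0.020 | 0.47 v 0.61 | 0.021 | 0.45 v 0.59 |
| 0.5 | 0.007 | 0.47 v 0.75 | 0.008 | 0.45 v 0.74 |
| 0.7 | 0.001 | 0.47 v 0.93 | 0.001 | 0.44 v 0.91 |

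The paired tests hold their type I error at 0.049 to 0.051 throughout. The power of the unpaired tests barely changes with ρ, so they gain almost nothing from the design.

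**Step 5: skewed data.** The plan reserves Mann-Whitney for non-normal data, so the rank comparison was repeated on lognormal data, with d and ρ set on the underlying normal scale. Power of Mann-Whitney v signed-rank is about 0.45 v 0.41 at ρ = 0, 0.44 v 0.52 at 0.3, 0.43 v 0.65 at 0.5 and 0.43 v 0.86 at 0.7. The gain from pairing is smaller at low ρ but remains large from 0.5 upwards.

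**Step 6: detectable difference.** With 80% power, a paired analysis detects (1.96 + 0.84)√(2(1-ρ)/30) SD by the normal approximation: 0.72 at ρ = 0, 0.61 at 0.3, 0.51 at 0.5 and 0.40 at 0.7.

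**The case against.** - **The form of the Student test is not stated.** This is true, and for normally distributed outcomes the fault is inferred from the companion test. The plan also does not say which outcomes fell into which branch, so the number of comparisons certainly affected is unknown. Mann-Whitney, however, is unpaired beyond doubt. If a paired t-test was meant, the two branches assume different designs and the text still needs correcting.
- **The Protocol could be read as parallel groups.** It says "Randomized, prospective, split mouth and single core, 30 patients in total were divided into two groups". The same sentence calls the study split-mouth, and the treatment description gives each patient both treatments, so this reading fails.
- **Normal-data figures overstate the loss for the rank test.** This stands in part. With lognormal data at ρ = 0.3, signed-rank gains about 8 points rather than about 14, and at ρ = 0 it is 4 to 5 points worse. For positive correlations of 0.3 and above the direction is unchanged.
- **The harm depends on an unknown correlation and is conservative.** Both points stand. Under positive correlation, a significant PRP-laser difference would not be undermined on this ground. Inflated type I error needs a negative correlation, which is not the expected case and carries no weight in the conclusion. The mismatch between test and design does not depend on ρ.
- **The chi-square point is speculative.** The Protocol defines no categorical outcome compared between sides, so the point applies only if there is one.

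**Conclusion.** The concern holds and must be fixed. As written, the plan analyses 30 within-patient pairs with a test for independent samples: certainly in the Mann-Whitney branch, and on the natural reading in the Student branch. Nothing else in the plan makes the PRP-laser comparison a paired one.

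The size depends on the assumed correlation and effect. For normal data and a 0.5 SD difference, the unpaired t-test gives up about 14 percentage points of power at ρ = 0.3, 28 at 0.5 and 46 at 0.7, and essentially none at ρ = 0. The practical consequence is that a non-significant PRP-laser result from the stated tests cannot be taken as evidence of little difference.

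**What to change.** Compare the treatments within patients:

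- Use a paired t-test on the PRP-minus-laser difference, or the Wilcoxon signed-rank test if the differences are clearly non-normal. Apply Shapiro-Wilk and the histograms to the differences, not to each treatment separately.
- An acceptable alternative is a mixed model with a random patient effect and fixed terms for treatment, period (first or second surgery) and side, since order and side were randomised.
- If a yes/no outcome is compared between sides, name it and use McNemar's test.
- State the form of the t-test explicitly, and reword the Study Protocol sentence about dividing patients into two groups so that it says each patient receives both treatments.

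The cost is a change to the text and, because the plan is written in the past tense, re-running and re-reporting any between-treatment comparisons already done. No new data are needed, because both sides are recorded in the same patients. If the correlation proves to be zero, the paired t-test loses about one percentage point of power with normal data (0.478 v 0.466), and the signed-rank test loses 4 to 5 points with lognormal data.

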The patients were checked in the first session they came to, and on the 2nd and 7th days after the operation. After the operation in all patients; Amoxicillin 1000mg (Largopen 1000mg,2*1 (Bilim Ilac Sanayii Ve Ticaret A.S. Istanbul, Turkey), Dexketoprofen 25mg (Arveles 25mg, 2*1 (Menarini, Istanbul, Turkey)), benzylamine HCl + chlorhexidine gluconate gargle (Andorex 200ml gargle, 3*1 (Humanis Sağlık A.S. Istanbul, Turkey) were used routinely. Sutures were removed after 1 week. Pain was assessed with Visual Analog Scale (VAS) at 3, 6, 9, 12 and 24 hours and on days 2, 3, 4, 5, 6 and 7. Angulus-tragus, angulus-lateral canthus, angulus-nasalis, angulus-labial commissure and angulus-pogonion points were used to evaluate edema. Measurements were made immediately before, 2 days after and 7 days after the operation. For the evaluation of trismus, mouth opening - the distance between the incisal edges of the central teeth during maximum mouth opening - was measured immediately before, 2 days after and 7 days after the operation. As a result, statistical analysis was performed and interpreted for the

obtained data. Before surgical extraction of the impacted tooth, the inferior alveolaris and buccal nerve were local anesthetized and the buccal flap was elevated mucoperiosteally with a 'Winter' incision using a scalpel number 15. A 1.6 mm diameter steel carbide round cutter, fissure cutter burs, a surgical micromotor operating at 1400 rpm and serum irrigation were used to remove the bone. The teeth were exposed. The teeth were then divided into two by bur and extracted with the help of a dental elevator. During the operation, 2 ampoules of local anesthetic (Ultracain 69 DS forte-Aventis İlaç Sanayi Tic. A1, Turkey) containing 40 mg/ml articaine HCl and 0.012 mg/ml epinephrine HCl were used as local anesthetic solution in all groups. The flap was closed primarily with 3/0, 19 mm atraumatic silk sutures and 3/8 round needles. The time between the first incision and the last suture was calculated and recorded.

Statistical Analysis Plan

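### The PRP-versus-laser tests name neither the randomised surgery order nor the preoperative edema values, and the plan names no treatment-by-time contrast

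*Combined protocol and SAP*

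**What the plan says.** The Statistical Analysis Plan is one paragraph. On the treatment comparison: "Comparisons between the two treatment groups were made with the Student-T test for data suitable for normal distribution"; Mann-Whitney U covers the rest. On the time course: "In order to find statistical differences in the time-dependent changes in the measured data in both treatment groups, repeated measures ANOVA test was used". That applies where the data look normal, with Bonferroni post-hoc tests; on the other branch, "Friedman test was applied to non-normally distributed data and Dunn-Bonferroni test was used for post-hoc comparisons". No covariate, change score, order or period term, or interaction is named.

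The Study Protocol shows what is available:

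- Order: "It was randomly determined which material would be used first on which side". The second side follows after 2 weeks.
- Edema: "Angulus-tragus, angulus-lateral canthus, angulus-nasalis, angulus-labial commissure and angulus-pogonion points were used to evaluate edema". The protocol then gives the timing, which includes a preoperative reading: "Measurements were made immediately before, 2 days after and 7 days after the operation".
- Mouth opening: "the distance between the incisal edges of the central teeth during maximum mouth opening", at the same three times as edema.
- Pain: "Pain was assessed with Visual Analog Scale (VAS) at 3, 6, 9, 12 and 24 hours" and daily from day 2 to day 7, which makes 11 times, none of them before surgery.

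**The concern.** The design randomises an order and collects preoperative values, but the test that compares the treatments names neither. If first and second operations differ systematically, that difference inflates the error, and a chance imbalance in order moves the estimate. Side-to-side edema differences present before surgery and persisting to day 2 or day 7 also stay in the error.

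The time course is a separate gap. The visit schedule invites statements that one treatment recovers faster, yet no named test addresses them. Friedman is a one-way test over time and has no treatment-by-time term. A reader would be left to compare which visits, or which within-arm tests, reached significance, and such patterns can differ by chance.

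**Working it through.** **Inputs.** From the documents: 30 patients, split mouth, order randomised, significance at 0.05 (taken as two-sided). The plan gives no power, SD, effect size or correlation, so there is no stated figure to reproduce. Assumed: SD 1 per side, between-side correlation 0.5, true difference 0.5 SD. The SD of the within-patient difference is then √(2(1 − 0.5)) = 1. A paired t-test has noncentrality 0.5 × √30 = 2.74 on 29 df, hence 75% power.

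**Order.** Let p be the first-versus-second-surgery difference, in SD. The PRP-minus-laser difference is shifted by +p in one order group and −p in the other. Without an order term:

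- Shift of the estimate = p(n₁ − n₂)/n. At 15:15 it is 0. At 18:12 it is 6/30 = 0.2p, so with p = 0.5 a true 0.50 reads 0.60 or 0.40, depending on direction.
- Estimated SE at 15:15 is inflated by √(1 + p²), or 1.12 at p = 0.5.

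Simulated power of the paired test at 15:15:

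| p (SD) | without order | with order |
|---|---|---|
| 0 | 75% | 75% |
| 0.2 | 74% | 75% |
| 0.5 | 67% | 75% |
| 0.75 | 57-58% | 75-76% |

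At 18:12 with p = ±0.5, power is 84% or 47% without order and 74% with it. Type I error of the paired test stays near 5% at 18:12. At 15:15 with p = 0.5 it falls to about 3%. Under simple randomisation (the method is not stated), a split of 18:12 or worse has binomial probability 0.36.

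**Preoperative edema value.** Let r be the correlation between the preoperative and postoperative within-patient differences. Residual variance is multiplied by 1 − r², so noncentrality becomes 2.74/√(1 − r²): 2.87, 3.16 and 3.83 at r = 0.3, 0.5 and 0.7, before the small cost of the extra terms. Simulated power with order and the uncentred preoperative difference, against 75% with order alone:

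| r | power |
|---|---|
| 0 | 73-74% |
| 0.3 | 77-78% |
| 0.5 | 85% |
| 0.7 | 95% |

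Type I error is about 5%. This r is lower than the raw pre-post correlation. If the raw value is 0.7 and all correlations across sides are 0.5, then r = (0.7 − 0.5)/(1 − 0.5) = 0.4 and power is about 80-81%.

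**Other outcomes.** Pain has no preoperative value. Mouth opening is one distance per patient, so its stable level cancels in the within-patient difference. Its second preoperative value also follows the first operation: if the residue of that operation differs by 0.2 SD between treatments, adjusting shifts the estimate by 0.03-0.05 SD (type I error 5.3-6.0%), against no shift without the term.

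**Time course.** Suppose the true difference is 0.5 SD at both day 2 and day 7, so nothing changes. The results depend on the between-time correlation:

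| | correlation 0.5 | correlation 0.8 |
|---|---|---|
| Unpaired tests disagree on significance | 34% | 21% |
| Order-adjusted paired tests disagree | 26% | 16-17% |
| Direct day-2-to-day-7 contrast rejects | 5% | 5% |

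If the difference exists at day 2 only, the direct contrast has 75% or 99% power.

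**Comparator.** The unpaired t-test, read literally and under the same assumptions at 15:15, has 43-47% power for period effects up to 0.5 SD and a type I error of about 0.5-0.7%. The step from there to a paired analysis is due to pairing, not to order or baseline.

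**The case against.** A randomised comparison without covariates is valid, and much of the gain here is modest or conditional. Order adds about 1 point at a 0.2 SD period effect, and the 18:12 shift needs both an imbalance and a period effect that the documents do not show. The baseline gain is between about −2 and +3 points up to r = 0.3; larger gains are arguable for edema alone. All of this stands and limits the weight of the point.

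Three stronger readings are tempting. A reader might infer that omitting order biases the comparison; because order was randomised, it does not do so systematically. A reader might infer that treatments are compared only through within-arm tests; the plan names direct between-treatment tests, and its ANOVA wording may cover a group factor. A reader might charge the low power of the unpaired test to these omissions; most of that loss is the missing pairing, a separate matter.

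It is also fair that no passage states a recovery-speed claim, that the plan does not say at which times the treatments are compared, and that disagreement between visits mostly survives the fix. The last point is why a direct contrast is needed: better visit tests do not replace it. Finally, the plan names no primary outcome, and this change supplies neither one nor a multiplicity rule.

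**Conclusion.** The point holds in limited form: three omissions in the plan that should be corrected, none of which makes the treatment comparison invalid. The clearest is the missing treatment-by-time contrast, certain on the Friedman branch and unstated on the ANOVA branch. Order is a refinement worth up to 8 points of power at period effects up to 0.5 SD, and it protects against a shift of 0.2 times the period effect at 18:12. The preoperative term is justified for edema only; nothing in the documents supports asking for it in pain, and for mouth opening it may do slight harm. Every magnitude depends on the assumed 0.5 SD difference, the correlations and the period effects, so confidence in the sizes is medium. Confidence that the terms are not named is high.

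**What to change.** Write into the Statistical Analysis Plan:

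1. For each outcome and visit, regress the within-patient PRP-minus-laser difference on surgery order coded +0.5/−0.5. The intercept is the treatment effect.
2. For edema only, add the preoperative PRP-minus-laser difference, not centred at its sample mean. Use no preoperative term for pain or mouth opening in the main analysis.
3. Test any claim that recovery differs by the same order-adjusted analysis of the day-2-to-day-7 change in the within-patient difference. For pain, use one prespecified early-minus-late contrast, for example the mean of the five times up to 24 hours minus the mean of days 2-7. Do not infer it from which visits or within-arm tests are significant; with a constant difference, visit tests can still disagree in about 16-26% of trials.
4. For non-normal data, take the first-minus-second-surgery difference of the visit value or contrast and compare it between the two order groups by Mann-Whitney; half the Hodges-Lehmann shift estimates the treatment difference. For edema visits, use Quade's rank analysis of covariance with the preoperative difference, with no change-score alternative. At r = 0.3, Quade's method has 75% power against 57% for the change score; at r = 0, 71% against 43%.
5. Report within-arm time tests descriptively.

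The document is worded in the past tense. If the data have already been analysed, add these results and label them as later additions.

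Cost: wording and a few regressions on data already collected, two or three degrees of freedom, and about 1-2 power points per term if there is no period effect or no pre-post correlation.

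### The pain-over-time tests use only patients with all 11 VAS scores for a treatment and, as worded, name no treatment-by-time test; a mixed model for VAS would address both

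*Combined protocol and SAP*

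**What the plan says.** The Study Protocol sets the pain schedule: "Pain was assessed with Visual Analog Scale (VAS) at 3, 6, 9, 12 and 24 hours", then once daily from day 2 to day 7. Postoperative checks take place "on the 2nd and 7th days after the operation". The sample is 30 patients in a split-mouth design, so each patient should supply one pain series after PRP and one after laser.

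For change over time in the two treatment groups, the Statistical Analysis Plan states that "repeated measures ANOVA test was used for normally distributed data", with Bonferroni comparisons afterwards. Where normality fails, "Friedman test was applied to non-normally distributed data", with Dunn-Bonferroni comparisons afterwards. The PRP-versus-laser comparison is assigned to other tests: Student's t or Mann-Whitney.

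The plan gives no rule for a missed score, no imputation, no analysis set and no expected missing rate. The nearest text is the exclusion of patients who fail to attend check-ups. That does not cover a single pain score missed between visits.

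**The concern.** Repeated-measures ANOVA and Friedman both work on complete rows. With 11 scores per row, one gap discards the 10 scores that were recorded, so modest missingness can cost many patients. Nine of the 11 times do not coincide with a scheduled check, and those are the scores most exposed to being missed.

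The second weakness does not depend on missing data. Showing that pain changes over a week within each treatment does not show that the two pain courses differ. That question needs a treatment-by-time term. The plan's wording names none, and Friedman, with a single repeated factor, cannot give one. At stake are the precision and the patient base of the pain-over-time analysis, and whether it answers the comparative question at all.

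**Working it through.** **Plan's own figure.** The sample size of 30 comes with no power, effect size, SD or dropout allowance, so there is no derivation to reproduce.

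**Inputs from the Study Protocol.**
- VAS times: 5 in the first 24 hours + 6 daily = 11 per operation.
- Times on a scheduled check: days 2 and 7, so 11 − 2 = 9 fall outside one.
- Patients: 30, giving 30 × 11 = 330 planned scores per treatment.

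**Assumption, not in the documents.** Each missable score is absent independently with probability q, from 1% to 10%.

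**Step 1: effect of one gap.** In a simulated 30 × 11 data set with one empty cell, a standard repeated-measures ANOVA routine rejected the data as unbalanced, and Friedman returned no result until the incomplete patient was removed. Both then ran on 29 patients, using 29 × 11 = 319 of the 329 observed scores. The ANOVA error degrees of freedom fell from 29 × 10 = 290 to 28 × 10 = 280. A mixed model kept all 30 patients and all 329 scores. These were general-purpose routines rather than SPSS, but the need for complete rows belongs to the methods.

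**Step 2: expected complete series.** The formula is 30 × (1 − q)^k, where k is the number of missable scores. Patients who miss check-ups are excluded, so k = 9 is the fairer base for one treatment. The table adds k = 11 (any score can be missed) and k = 18 (both sides entered in one ANOVA, so a gap on either side drops the patient).

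| q | k = 9 | k = 11 | k = 18 |
|---|---|---|---|
| 1% | 27.4 | 26.9 | 25.0 |
| 2% | 25.0 | 24.0 | 20.9 |
| 3% | 22.8 | 21.5 | 17.3 |
| 5% | 18.9 | 17.1 | 11.9 |
| 10% | 11.6 | 9.4 | 4.5 |

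At 5% with k = 9: 30 × 0.95^9 = 30 × 0.630 = 18.9, a loss of 37%. The expected number of missing scores is 30 × 9 × 0.05 = 13.5, so 316.5 of 330 are observed. The tests would use 330 × 0.630 = 208 of them.

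**Step 3: does any mixed model do?** No. Random intercepts alone imply one common variance from 3 hours to day 7. Suppose the SD falls evenly from 2.5 to 0.8 over the 11 times (an assumption). The mean SD is 1.65 and the variance of the 11 SDs is 0.17² × 10 = 0.289, so the average variance is 1.65² + 0.289 = 3.01 and the pooled SD is 1.735. A nominal 95% interval at the first time then has half-width 1.96 × 1.735 / 2.5 = 1.36 true standard errors, which is about 82% to 83% coverage. At the last time it is 1.96 × 1.735 / 0.8 = 4.25, about 100%. Simulation gave about 82% and about 100%. In separate simulations with 30 patients, no true effect and AR(1) correlation within side, the random-intercept treatment-by-time test rejected 7.7% (correlation 0.5) to 9.7% (correlation 0.7) of the time at nominal 5%.

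An unstructured covariance goes too far the other way: 11 × 12 / 2 = 66 parameters per side, or 22 × 23 / 2 = 253 across both, from 30 patients. Heterogeneous AR(1) needs 11 variances + 1 correlation = 12.

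**The case against.** The strongest reply is that no missing data are documented. The text is written in the past tense, so the real number of gaps is presumably known and may be zero, in which case the complete-case argument disappears. That stands: the sizes above are conditional. Independence is also a pessimistic assumption, since gaps that cluster in a few patients cost fewer series.

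Several stronger readings are tempting but unsupported:

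- A reader might infer that one missed score removes the patient from the PRP-versus-laser comparison, or that unequal subsets break the split-mouth comparison. That comparison is assigned to t or Mann-Whitney tests. Applied time by time, they keep the patient wherever a score exists. Their disregard of pairing is a separate matter.
- A reader might infer that scores were kept at home, that gaps were likely, or that completers had easier recoveries. The Study Protocol does not say where or how VAS was recorded, and nothing shows any of these.
- A reader might take k = 11 as the headline (17.1 of 30 at 5%). Since check-up attendance is required, the day 2 and day 7 scores should rarely be missing, and 18.9 is fairer.
- A reader might conclude that the ANOVA is certainly run within each treatment and can never compare the curves. The wording suggests separate analyses but does not rule out a treatment factor. Only for Friedman is the limitation certain.
- A reader might extend the missing-data argument to edema and trismus. Each is measured three times, just before surgery and on the two check-up days, and no comparable loss is shown.

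It is also fair to object that a mixed model with random intercepts only could be worse than what it replaces. That stands, and the covariance must be specified accordingly.

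**Conclusion.** The point holds for the VAS time-course analysis and no further. The named tests require all 11 scores for a treatment, the plan offers nothing to offset the loss, and as worded it names no treatment-by-time test. The expected number of complete series per treatment is about 25.0, 18.9 or 11.6 of 30 at assumed missing rates of 2%, 5% or 10% per score. This rests on independent misses at the 9 off-check times; the true loss could be nil. The change is worth making because the missing treatment-by-time comparison remains even if every score was collected. The documents name no primary outcome, so an effect on a primary analysis is not shown.

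**What to change.** For VAS only, replace the repeated-measures ANOVA and Friedman tests with one likelihood-based linear mixed model in SPSS, using all available scores:

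- Fixed effects: treatment, time (11 levels), treatment-by-time and surgery order.
- A patient random effect.
- A pre-specified residual covariance within each patient-side that lets variance differ by time and correlation fall with lag, for example heterogeneous AR(1). The times are unevenly spaced (3-hour steps at first, daily steps later), so state that lag is counted in visit order if this structure is used.
- Satterthwaite degrees of freedom.

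Report the PRP-minus-laser difference with 95% CI at each time. Check it against within-patient paired differences at each time, or a patient-level bootstrap. Report the number of complete VAS series per side, so that readers can see how much the plan's own tests would have discarded.

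The cost is a few lines of SAP text and modest analysis work, with no new data. There are two small downsides: the covariance structure must be chosen in advance, and the model assumes that scores are missing at random.
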